3. INVESTIGATIONAL PLAN

3.1. Study Design

Double-blind, randomized, placebo-controlled trial in subjects with ITP who are 'non-responders' at the maximum package insert dose (75mg) of eltrombopag; non-responders are those with platelet counts $< 50,000$ despite taking 75 mg/day of eltrombopag for at least 3 weeks.

Study Design (First part): 8 Weeks

Informed consent and assent of minors will be obtained by the principal investigators or sub-investigators. Typically, informed consent/minor assent will be obtained in the outpatient clinic, although inpatients may have this discussed with them as well. Consent will be obtained after review of clinical information and satisfaction of eligibility criteria. Subjects will be randomly allocated at a two to one ratio to receive active treatment or placebo. All subjects must be ≥ 3 years old and able to swallow a tablet. in the study will receive 75 mg eltrombopag and then be randomized to receive either an additional 25 mg of eltrombopag or matching placebo tablet dispensed by the research pharmacy

Subjects and investigators will be blinded to randomization. Randomization will be stratified according to splenectomy status. Randomization will be performed at the time of informed consent with a computer generated randomization table as per the pharmacy. Subjects may enroll and begin taking 75 mg eltrombopag for at least 3 weeks. When subject's platelet count is $< 50,000$, the subject may begin day 1 of the study. Subjects and investigators will be blinded to assignment and treatment in this phase. Eltrombopag will be administered for 8 weeks or until the platelet count exceeds 100,000; at this point dosing will stop, subject will be considered a responder and the subject will eligible for entering Part 2 (the long term treatment part of the study) if desired and agreed to be appropriate by the subject giving consent, and the treating physician. The dose at which the subject achieved the primary endpoint ($> 50,000$ and increase by $> 20,000$) will be considered the dose of response. Even if a patient achieves a response, if the platelet counts remains $< 100,000$, then the dose escalation schema in the figure above will continue.

[figure not shown]

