4. SUBJECT SELECTION AND WITHDRAWAL CRITERIA

4.1. Number of Subjects:

60 subjects will be enrolled.

4.2. Inclusion Criteria:

Subject or their parent/ guardian has signed and dated a written informed consent

Males and Females aged 3 year or older, who can swallow a tablet, and are diagnosed with chronic ITP according to the new consensus guidelines (Provan, Blood, 2009) are eligible.

No indication of a disease which may cause thrombocytopenia other than ITP---- no specific testing required

Subjects with thrombocytopenia $\leq 50,000 /uL$ after at least 21 days of daily dosage with eltrombopag 75mg

Stable dosage of concomitant treatments for ITP
 ≥ 2 weeks or longer (corticosteroids);

At least 2 weeks from rescue therapy for ITP (WinRho, IVIG, corticosteroids, platelet transfusion) or 1 week if therapy has clearly been ineffective

At least 4 weeks from rituximab treatment

Pregnant or Lactating Women are excluded

Women of child-bearing age with a negative pregnancy test within 7 days of enrollment and who agree to use acceptable methods of birth control will be eligible for this study

Female subjects or female partners of male subjects must either be of non-child bearing potential (hysterectomy, bilateral oophorectomy , bilateral tubal ligation or post menopausal for more than one year) OR, if of child bearing potential, using one of the following highly effective methods of contraception.
-complete abstinence from intercourse

- Intrauterine device (IUD)
- Two forms of barrier contraception. diaphragm plus spermicide, or for males condoms plus spermicide.
- Male partner is sterile and is the only partner of the female.
- Systemic contraceptives

4.3. Exclusion Criteria:

Previous history of eltrombopag-related LFT elevation that required sustained interruption of treatment

Previous history of immediate or delayed hypersensitivity reaction or idiosyncrasy to drugs chemically related to eltrombopag

Known HIV Infection

History of Arterial or Venous Thrombosis within the past year or requiring ongoing therapy

Known Active Hepatitis C infection

Elevated AST/ALT or Creatinine > 1.5 times upper limit of normal in 4 weeks prior to enrollment*

Abnormalities in WBC, ANC and Hemoglobin > 1.5 times upper or lower limit of normal*

* Subjects can be rescreened to be included

4.4. Withdrawal Criteria:

Subject may withdraw consent at any time

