If new or worsening blood morphological abnormalities or cytopenias occur, a bone marrow biopsy should be considered, including staining for fibrosis..

Thrombotic/thromboembolic complications

Thrombotic/thromboembolic complications may result from increases in platelet counts with eltrombopag and those reported in controlled clinical studies in patients with chronic ITP included both venous and arterial events and were observed at low and normal platelet counts.

Use caution when administering eltrombopag to patients with known risk factors for thromboembolism (e.g., Factor V Leiden, ATIII deficiency, antiphospholipid syndrome, chronic liver disease). To minimize the risk for thrombotic/thromboembolic complications, do not use eltrombopag in an attempt to normalize platelet counts. Follow the dose adjustment guidelines to achieve and maintain a platelet count of $\geq 50 \times 10^9/L$ as necessary to decrease the risk for bleeding

In a placebo-controlled double-blind study (ELEVATE) of 292 patients with chronic liver disease who were undergoing an elective surgical procedure, the risk of portal venous thrombosis was increased in patients treated with 75 mg eltrombopag once daily for 2 weeks in preparation for their invasive procedure. Seven thrombotic complications (six patients) were reported within the group that received eltrombopag and three thrombotic complications were reported in the placebo group (two patients). All of the thrombotic complications reported within the eltrombopag group were of the portal venous system. Five of the six patients in the group that received eltrombopag experienced a thrombotic complication within 30 days of completing treatment with eltrombopag and at a platelet count above $200 \times 10^9/L$. Malignancy is known to increase the risk for developing a thrombotic event and four of the 6 patients either had a diagnosis or suspicion of malignancy (2 hepatocellular carcinoma; 1 possible lymphoma and 1 brain tumor).

Caution should be exercised when administering eltrombopag to patients with hepatic impairment (Child-Pugh Class A, B, C) and a lower starting dose of eltrombopag should be used in patients with any degree of hepatic impairment. Such patients should be monitored very closely. Eltrombopag is not indicated for the treatment of thrombocytopenia in patients with chronic liver disease.

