- Must return weekly for repeat liver chemistries (ALT, AST, alkaline phosphatase, bilirubin) until they resolve, stabilize or return to within baseline values
- If at any time the subject meets any of the liver chemistry stopping criteria 1 – 5, proceed as described above
- If, after 4 weeks of monitoring, ALT <3x ULN and bilirubin <2x ULN, monitor subjects twice monthly until liver chemistries normalize or return to within baseline values.

Protocol Stopping Rules

Novartis and the Principle Investigator may terminate the study at any time. Early termination may occur due to emergent risk information or the decision by Novartis to discontinue the development of Eltrombopag.

Dose Escalation Rules

In Part 1 of the study, subjects will be randomly allocated at a two to one ratio to receive active treatment or placebo. All subjects in the study will receive 75 mg eltrombopag and then be randomized to receive either an additional 25 mg of eltrombopag or matching placebo tablet dispensed by the research pharmacy.

Eltrombopag will be administered bi-weekly for 8 weeks. If platelet count does not exceed 100,000, the additional eltrombopag or matching placebo tablet will be increased by 25 mg until the patient receives 75 mg eltrombopag and 75 mg eltrombopag or matching placebo (100mg x 2 weeks, 125 mg x 2 weeks, 150 x 4 weeks). If the patient's platelet count exceeds 100,000 during part 1 dosing will stop, subject will be considered a responder, and the subject will eligible for entering Part 2 (the long term treatment part of the study).

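### Section 4.3 does not exclude known hepatic impairment, although 6.4 advises caution and a lower starting dose there and Part 1 escalates to 150 mg with no hepatic branch

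*Combined protocol and SAP*

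**What the plan says.** **Safety advice (6.4, thrombotic complications).** For Child-Pugh A, B or C impairment the text urges caution and very close monitoring, and adds that "a lower starting dose of eltrombopag should be used in patients with any degree of hepatic impairment". It also states that "Eltrombopag is not indicated for the treatment of thrombocytopenia in patients with chronic liver disease" and names chronic liver disease among the known thromboembolic risk factors. It describes a placebo-controlled trial in 292 patients with chronic liver disease having elective procedures, in which "the risk of portal venous thrombosis was increased in patients treated with 75 mg eltrombopag once daily for 2 weeks".

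**Entry rules (4.2, 4.3).** The criteria that bear on the liver are:
- the inclusion line "No indication of a disease which may cause thrombocytopenia other than ITP---- no specific testing required";
- the exclusion "Elevated AST/ALT or Creatinine > 1.5 times upper limit of normal in 4 weeks prior to enrollment", with the footnote "Subjects can be rescreened to be included";
- known active hepatitis C;
- an earlier eltrombopag-related liver-test elevation that led to sustained interruption.

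No line names hepatic impairment, cirrhosis or chronic liver disease, and none limits bilirubin. Fractionated bilirubin is nevertheless part of the screening chemistry (3.1 and 6.1).

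**Dosing (3.1, 6.3, Dose Escalation Rules in 6.4.6).** Everyone takes 75 mg. The active arm then follows "100mg x 2 weeks, 125 mg x 2 weeks, 150 x 4 weeks" unless the platelet count reaches the 100,000 ceiling or a stopping or withdrawal rule applies. Section 3.1 also allows that "Subjects may enroll and begin taking 75 mg eltrombopag for at least 3 weeks".

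**The concern.** The protocol identifies a group that needs a lower start and closer watching, then writes entry and dosing rules that do not mention that group. A subject with impaired liver function and near-normal transaminases could meet every criterion and be taken to 150 mg. That is twice the daily dose at which 6.4 reports more portal venous thrombosis in chronic liver disease. What is at stake is the safety of individual subjects, and consistency between the safety section and the rules that sites follow.

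**Working it through.** The plan gives no figure to reproduce here, so the check sets the sections side by side.

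1. **Do the entry rules screen for impairment?** Only in part. The AST/ALT limit picks up liver-cell injury rather than impaired function. The hepatitis C line covers one cause. The history line covers only earlier drug-related elevations. The 4.2 line asks about other diseases that may cause thrombocytopenia. It would probably keep out overt cirrhosis, but it names no liver disease and asks for no testing.

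2. **Do the dosing rules adapt?** No. In 3.1, 6.3 and the Dose Escalation Rules, escalation depends on the platelet count and the general stopping and withdrawal rules. Placebo non-responders may later follow the same escalation open label.

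3. **Who is in direct conflict with the starting-dose advice?**
   - A subject who enrols and first begins 75 mg in the 3.1 run-in: direct conflict, because no lower start is offered.
   - A subject already on 75 mg for 21 days or more: the starting dose is in the past. The caution and monitoring advice still applies, and no entry or dosing rule reflects it.

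4. **What would catch a problem on treatment?**
   - Part 1: chemistry every 2 weeks (3.1, Appendix 1), and dosing stops at the 100,000 ceiling.
   - Section 8.3.1.2: bilirubin above 2 x ULN, even alone, is assessed for continuing or stopping the drug.
   - Section 6.4.1: all five liver stopping criteria require ALT of at least 3 x ULN, so impaired function with normal ALT does not trigger them.
   - Section 4.4: withdrawal for a new thrombotic event or drug-induced liver injury.
   - Part 2: the dose is adjusted between 150,000 and 400,000 and the drug held above 400,000, but the investigator may decide not to reduce or stop (Dose Escalation Rules).

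5. **How large is it?**
   - Peak dose: 150 / 75 = 2.0 times the daily dose in the liver-disease trial.
   - Events in that trial: 6 eltrombopag patients and 2 placebo patients with thrombotic complications among 292. Arm sizes are not given, so no rates can be formed.
   - Five of the 6 had platelet counts above 200 x 10^9/L. That is twice the Part 1 ceiling (200,000 / 100,000) and lies inside the Part 2 adjustment band.
   - Four of the 6 had diagnosed or suspected malignancy.
   - The documents give no prevalence of impairment. As an assumption only, let p be its share among otherwise eligible subjects. With 60 x 2/3 = 40 on active drug, the chance of at least one is 1 - (1 - p)^40: 0 at p = 0, 0.331 at p = 1%, and 0.871 at p = 5%.

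6. **Does it touch the statistics?** No. A hepatic exclusion changes none of the sample-size inputs (50% against 5% response, 80% power, two-sided 5%, 2:1) and no endpoint.

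**The case against.** The best reply is that the gap is already mostly covered. Section 6.4 itself treats chronic liver disease as a setting for thrombocytopenia, so the 4.2 line should remove known disease. A new line for known impairment would require no more testing than that one does. This stands in part: for overt disease the new line mainly makes the rule explicit. It does not dispose of mild impairment in a subject whose low count is attributed to ITP, because 4.2 asks about the cause of the thrombocytopenia and not about liver function.

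Second, the quoted advice concerns the starting dose, and 4.2 requires at least 21 days at 75 mg. Section 3.1 also places consent after eligibility is satisfied, so it is unclear how often a subject would first start on study. This stands, and it is why the direct conflict is limited to the run-in.

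Third, the on-treatment checks answer much of the call for close monitoring. That holds in Part 1. It is weaker in Part 2, where visits may fall to every 8 weeks and the list of tests for each visit in 3.1 does not include the chemistry panel. Appendix 1 has a chemistry row for Part 2, though no visits are marked in the text available.

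Two stronger readings are tempting, and the documents support neither.
- A reader might total the milligrams (14 x 100 + 14 x 125 + 28 x 150 = 7,350 mg for a full active course, against 14 x 75 = 1,050 mg in the liver-disease trial) and take the ratio as a multiple of risk. Section 6.4 links thrombosis to platelet increases and says nothing about cumulative dose.
- A reader might carry the liver-disease trial's excess over to this trial. Those patients were having elective procedures and most of those affected had known or suspected malignancy, whereas subjects here enter with counts of 50,000 or less on 75 mg.

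**Conclusion.** The point holds as a minor inconsistency between the safety section and the entry and dosing rules. Confidence is high that the text is missing, and much lower that any subject would be harmed as a result. The direct conflict with the starting-dose advice is confined to the run-in; otherwise the conflict is with the advice on caution. The existing safeguards reduce the exposure but leave open impaired function with near-normal transaminases. The number affected is unknown and may be zero. Efficacy results and sample size do not change. The conclusion assumes that the 6.4 advice is meant to apply to subjects of this trial, which its place in the protocol's own safety section supports.

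**What to change.** Add one exclusion to 4.3: **Known hepatic impairment (Child-Pugh A, B or C).**

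Optionally, extend the laboratory exclusion with a limit on direct bilirubin, keeping the 4-week window and the rescreening footnote. The sponsor should set the cut-off. One example is total bilirubin above 1.5 x ULN with a direct fraction above 35%: the 1.5 echoes the AST/ALT limit and the 35% echoes liver stopping criterion 1 in 6.4.1. The documents do not validate that combination as an entry rule. Requiring a raised direct fraction is meant to avoid excluding subjects for the indirect bilirubin rise that 6.4 reports as more frequent on eltrombopag.

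The cost is one new line, or one new and one extended line. No new test is needed, because fractionated bilirubin is already drawn at screening. A few candidates may be lost. No change to endpoints, analyses or sample size follows.

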6.4.1. Liver chemistry stopping and follow-up criteria

Liver chemistry stopping criteria and follow up requirements have been designed to assure subject safety and evaluate liver event etiology in alignment with the FDA Guidance for Industry – Drug-Induced Liver Injury: Premarketing Clinical Evaluation (July 2009, www.fda.gov).

Liver chemistry stopping criteria 1-5 are defined as follows:

1. ALT \geq 3x ULN and bilirubin \geq 2x ULN (>35% direct bilirubin) (or ALT \geq 3x ULN and INR $>$ 1.5, if INR measured)

NOTE: If serum bilirubin fractionation is not immediately available, study drug should be discontinued if ALT \geq 3x ULN and bilirubin \geq 2x ULN. Serum bilirubin fractionation should be performed if testing is available. If testing is unavailable, record presence of detectable urinary bilirubin on dipstick, indicating direct bilirubin elevations and suggesting liver injury.

1. ALT \geq 5x ULN
2. ALT \geq 3x ULN if associated with symptoms (new or worsening) believed to be related to hepatitis (such as fatigue, nausea, vomiting, right upper quadrant pain or tenderness, or jaundice) or believed to be related to hypersensitivity (such as fever, rash or eosinophilia).
3. ALT \geq 3x ULN persists for \geq 4 weeks

4. ALT \geq 3x ULN and cannot be monitored weekly for 4 weeks

When any of the liver chemistry stopping criteria 1 - 5 is met, do the following:

- Immediately discontinue study treatment
- Report the event to Novartis within 24 hours of learning its occurrence
 - All events of ALT \geq 3x ULN and bilirubin \geq 2x ULN ($>35\%$ direct bilirubin) (or ALT \geq 3x ULN and INR > 1.5 , if INR measured; INR measurement is not required and the threshold value stated will not apply to subjects receiving anticoagulants), termed 'Hy's Law', must be reported as an SAE (excluding studies of hepatic impairment or cirrhosis).
 - NOTE: if serum bilirubin fractionation is not immediately available, study treatment should be discontinued if ALT \geq 3x ULN and bilirubin \geq 2x ULN. Serum bilirubin fractionation should be performed if testing is available. If testing is unavailable, record presence of detectable urinary bilirubin on dipstick, indicating direct bilirubin elevations and suggesting liver injury.
- Complete the liver imaging and/or liver biopsy eCRFs if these tests are performed
- Perform liver event follow up assessments, and monitor the subject until liver chemistries resolve, stabilize, or return to baseline values as described below
- Do not rechallenge with investigational product.

In addition, for subjects meeting liver stopping criterion 1:

- Make every reasonable attempt to have subjects return to clinic within 24 hours for repeat liver chemistries, liver event follow up assessments (refer to Section 0), and close monitoring
- A specialist or hepatology consultation is recommended
- Monitor subjects twice weekly until liver chemistries (ALT, AST, alkaline phosphatase, bilirubin) resolve, stabilize or return to within baseline values.

For subjects meeting any of the criteria 2 – 5:

- Make every reasonable attempt to have subjects return to clinic within 24-72 hrs for repeat liver chemistries and liver event follow up assessments (refer to Section 0)
- Monitor subjects weekly until liver chemistries (ALT, AST, alkaline phosphatase, bilirubin) resolve, stabilize or return to within baseline values;

subjects meeting criterion 5 should be monitored as frequently as possible

Liver Event Follow Up Assessments

For subjects meeting any of the liver chemistry stopping criteria 1 – 5, make every attempt to carry out the liver event follow up assessments described below:

- Viral hepatitis serology including:
 - Hepatitis A IgM antibody
 - Hepatitis B surface antigen and Hepatitis B Core Antibody (IgM)
 - Hepatitis C RNA
 - Cytomegalovirus IgM antibody
 - Epstein-Barr viral capsid antigen IgM antibody (or if unavailable, obtain heterophile antibody or monospot testing)
 - Hepatitis E IgM antibody
- Serum creatine phosphokinase (CPK) and lactate dehydrogenase (LDH).
- Fractionate bilirubin, if total bilirubin \geq 2x ULN.
- Obtain complete blood count with differential to assess eosinophilia.
- Record the appearance or worsening of clinical symptoms of hepatitis, or

hypersensitivity, such as fatigue, nausea, vomiting, right upper quadrant pain or tenderness, fever, rash or eosinophilia as relevant on the AE form.

- Record use of concomitant medications, acetaminophen, herbal remedies, other over the counter medications, or putative hepatotoxins, on the concomitant medications form.
- Record alcohol use on the liver event alcohol intake form.

The following assessments are required for subjects with ALT ≥ 3 x ULN and bilirubin ≥ 2 x ULN ($>35\%$ direct) but are optional for other abnormal liver chemistries:

- Anti-nuclear antibody, anti-smooth muscle antibody, and Type 1 anti-liver kidney microsomal antibodies
- Liver imaging (ultrasound, magnetic resonance, or computerized tomography) to evaluate liver disease.

Liver Chemistry Monitoring Criteria

For subjects with ALT ≥ 3 x ULN but <5 x ULN and bilirubin <2 x ULN, without hepatitis symptoms or rash, and who can be monitored weekly for 4 weeks, the following actions should be taken:

- Notify Novartis within 24 hours of learning of the abnormality to discuss subject safety
- Can continue study treatment
- Must return weekly for repeat liver chemistries (ALT, AST, alkaline phosphatase, bilirubin) until they resolve, stabilize or return to within baseline values
- If at any time the subject meets any of the liver chemistry stopping criteria 1 – 5, proceed as described above
- If, after 4 weeks of monitoring, ALT <3 x ULN and bilirubin <2 x ULN, monitor subjects twice monthly until liver chemistries normalize or return to within baseline values.

6.4.2. Adverse Events

6.4.2.1. Definition of an AE

An **Adverse Event (AE)** is any unfavorable or unintended effect on a research participant whether or not the event is deemed study-related. AEs include new or increased symptoms, diagnoses, lab results or changes to a pre-existing condition. AEs are monitored throughout the duration of a study and for a specified period after the completion of study procedures (e.g. 30 days after the last treatment).

6.4.2.2. Definition of a SAE

A **Serious Adverse Event (SAE)** includes death, life threatening events, hospitalization or prolongation of hospitalization, disability or incapacitation, overdose, congenital anomalies and any other serious events that may jeopardize the health or well-being of the subject or require medical or surgical intervention to prevent one of the outcomes listed in this definition.

